8.7 Safety Oversight

It is the responsibility of the Principal Investigator to oversee the safety of the study. This safety monitoring will include careful assessment and appropriate reporting of adverse events as noted above, as well as the construction and implementation of a site data and safety-monitoring plan. Medical monitoring will include a regular assessment of the number and type of serious adverse events. The safety oversight will be conducted via a single medical monitor. It is felt that this is sufficient for this trial as the overall risk to the subjects is very low based on the number of subjects to be recruited, the type of non-invasive monitoring to be performed, and the safety profile of the drug to be studied.

CONFIDENTIAL

This material is the property of the NYU School of Medicine and Langone Medical Center. Do not disclose or use except as authorized in writing by the study sponsor

Interventional Template Version: 28 APR 2017

Safety oversight will be under the direction of a medical monitor with appropriate expertise, [name], MPH. [name] is a Pediatric Infectious Diseases physician and Microbiologist at NYU with expertise in both of these fields. The medical monitor will meet with the PI and co-investigator at least semiannually to assess safety and efficacy data on each arm of the study. Data collected to date will be reviewed including participants' demographics, any significant history or illnesses, % change in colonization for nose and peri-rectal area, and answers to questionnaires. Safety data will also be reviewed including any adverse effects that have occurred, side effects reports and retention/dropout rate. The medical monitor will provide its input to the PI, IRB and industry partner.

9 Clinical Monitoring

Clinical site monitoring is conducted to ensure that the rights and well-being of human subjects are protected, that the reported trial data are accurate, complete, and verifiable, and that the conduct of the trial is in compliance with the currently approved protocol/amendment(s), with GCP, and with applicable regulatory requirement(s).

- Monitoring for this study will be performed by [name], MPH.
- Monitoring will be centralized at NYULMC and will occur at the initiation of the study and semi-annually throughout the duration of the study. On-site monitoring of Tisch Hospital will occur once at the initiation of the study. Targeted, random review of data collection, data recording, data handling, data analysis, study-related procedures, and safety monitoring will be performed. The monitoring reports will be distributed to the PI, co-investigators and the IRB within 30 days.
- Independent audits will not be conducted at this trial does not involve numerous sites
- Internal quality management of study conduct, data collection, documentation and completion will be performed centrally.

10 Statistical Considerations

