5.8 Premature Termination or Suspension of Study

This study may be temporarily suspended or prematurely terminated if there is sufficient reasonable cause. Written notification, documenting the reason for study suspension or termination, will be provided by the study investigators to the study team members, partnering sites, industry partner, and the IRB. If the study is prematurely terminated or suspended, the PI will promptly inform the IRB and will provide the reason(s) for the termination or suspension.

Circumstances that may warrant termination or suspension include, but are not limited to:

- Determination of unexpected, significant, or unacceptable risk to participants
- Demonstration of efficacy that would warrant stopping
- Insufficient compliance to protocol requirements
- Data that are not sufficiently complete and/or evaluable
- Determination of futility

Study may resume once concerns about safety, protocol compliance, data quality are addressed and satisfy the sponsor, IRB and/or FDA.

6 Study Agent (Study drug, device, biologic, vaccine etc.) and/or Procedural Intervention

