6.2 Study Agent Accountability Procedures

The study agents will be allocated and dispensed by the NYULMC Investigational Research Pharmacy. The pharmacy and research pharmacist will receive shipment of the agents, allocated into individual unidentifiable container and be responsible for the blinding of the agents. The dispensed drugs will be given to the PI or co-investigator in blinded fashion by the Investigational Pharmacy for enrolled patients at the time of enrollment visit. The PI/co-investigator will distribute the agents to the participants at study visit 1. The handling and distribution will be documented by the PI/co-investigator in locked and de-identified official study records. The participants will be asked to return containers at study visit 2 after completing the 5 day decolonization process at home. This will allow for drug reconciliation checks to document drug assigned, drug consumed and drug remaining. This reconciliation will be logged on the drug reconciliation form and signed and date by the study team. The returned containers will be collected by the study team and then returned to the NYULMC Investigational Research Pharmacy for final reconciliation and destruction on site.

7 Study Procedures and Schedule

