10.3 Analysis Datasets

This will be a triple-blinded randomized Intent to Treat (ITT) clinical trial to assess the effectiveness of retapamulin in children colonized with MRSA under the age of 18 from a pre-specified community in Brooklyn. Participants living in the following zip codes will be eligible: 11024, 11205, 11206, 11211, 11213, 11214, 11218, 11219, 11225, 11230, 11249. Neither the treatment team nor the subject will know the treatment assignments. The outcome will be a dichotomous variable (1 = Yes, patient's swab negative for MRSA, 0 = No, Patient's swab positive for MRSA). We will analyze additional co-variables collected on the data collection form such as age, gender, history of MRSA infections, history of chronic medical conditions/chronic skin conditions, etc. (see Data Collection Form in appendix uploaded into study-related documents).

Information from the data collection form will be entered into an Access database designed for this study to provide a readily electronic version dataset to analyze. The following variables will be included: Assigned group (blinded treatment arm, A/B), age, gender, side effects, application day 1 (Y/N), application day 2 (Y/N), application day 3 (Y/N), application day 4 (Y/N), application day 5 (Y/N), environmental clean (Y/N), history of medical conditions or chronic skin conditions, history of MRSA, history of MRSA in family, recent or concomitant antibiotic use, prior retapamulin use etc. Variables related to safety will also be recorded in the database.

In addition to the ITT analysis, we will conduct a per-protocol analysis of those who completed 4 or 5 days of treatment and analyze similar to the ITT analysis.

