10.4.7.2 Efficacy Review

Study enrollment and administration of study drug will be halted if serious adverse events are noted across multiple participants. If it was deemed that enrollment and administration of drug needed to be stopped, it would pertain to the entire study including participants in both arms. Interim analysis is not planned for efficacy review.

CONFIDENTIAL

This material is the property of the NYU School of Medicine and Langone Medical Center. Do not disclose or use except as authorized in writing by the study sponsor
Interventional Template Version: 28 APR 2017

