10.6 Measures to Minimize Bias

10.6.1 Enrollment/Randomization/Masking Procedures

In order to produce treatment groups in which the distributions of prognostic factors, known and unknown, are similar and minimize bias, we will randomize participants to treatment groups. We will generate a randomization schedule using SAS 9.3 (SAS Institute, Cary NC). Additionally, participants, investigator, treatment team and analyst will be blinded to treatment group. The generated randomization schedule will be provided to the research pharmacy who will assign which arm is the treatment groups and reveal assignment after analysis is complete. The pharmacy will carry out the blinding as the drugs (ointments) will be aliquoted into unmarked containers labeled with the arm (A or B). The research pharmacy will provided drug to the investigators when a subject is enrolled in blinded form. The A/B group identifier (retapamulin vs placebo) will not be revealed until the study is completed and data analyzed. There are no anticipated obvious drug effects from the retapamulin or placebo that would imperfect blinding.

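### Semiannual by-arm efficacy reviews with the PI and co-investigator contradict the blinding and the absence of an interim analysis, and are likely to reveal which of A and B is active

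*Combined protocol and SAP*

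**What the plan says.** Section 8.7 (Safety Oversight) says the medical monitor "will meet with the PI and co-investigator at least semiannually to assess safety and efficacy data on each arm of the study". The data reviewed include the percentage "change in colonization for nose and peri-rectal area", and the monitor's input goes to the PI, the IRB and the industry partner. Nothing in the section restricts the review to pooled data, to a closed session or to the monitor alone.

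Four other places bear on this:

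- **Blinding.** Section 10.6.1 states that "participants, investigator, treatment team and analyst will be blinded to treatment group" and that the key is withheld until the data have been analyzed. Section 10.3 calls the trial triple-blinded.
- **Interim analysis.** Section 10.4.7 marks it not applicable, and 10.4.7.2 says "Interim analysis is not planned for efficacy review".
- **Stopping.** Section 5.8 still lists "Demonstration of efficacy that would warrant stopping", and also futility, among possible grounds for ending the trial. The supplied text gives no boundary for either.
- **Coding.** Section 10.6.1 has the ointments "aliquoted into unmarked containers labeled with the arm (A or B", and 10.3 stores the variable "Assigned group (blinded treatment arm, A/B" in the study database.

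Section 6.2 adds: "The PI/co-investigator will distribute the agents to the participants at study visit 1".

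**The concern.** The two people whom 8.7 invites to see efficacy by arm are people whom 10.6.1 says are blinded. Calling the arms A and B protects the blind only while nobody can tell which letter is active. Accumulating colonization results by letter answer exactly that question if the drug works. Because only two letters serve the whole trial, and 10.6.1 puts them on the containers, a correct guess covers every past and future participant. The same coding undermines 10.6.3, which separates breaking the blind for one participant from breaking it for all. Disclosing one participant's treatment discloses the key.

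The PI and co-investigator are well placed to affect the result. They take part in recruitment (5.4) and consent (13.3.2), hand out the containers (6.2), hold the file linking study code to participant (13.4), and transfer results to the database as the trial proceeds (14.1). Study investigators process the cultures (7.1.1). Section 10.5 excludes participants who withdraw before the week-1 endpoint, so uneven follow-up effort would feed straight into the primary comparison. With 22 evaluable per arm, a handful of influenced decisions matters.

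A secondary risk is an informal stop. If a review led to stopping for efficacy without a boundary, the false-positive rate would rise and the reported effect would be exaggerated. Stopping for futility would cost power but would not inflate type I error.

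**Working it through.** **Inputs.** From 10.5: 60% vs 15% decolonization, Fisher's exact test at 0.05 (two-sided assumed, as sidedness is not stated), 22 evaluable per arm. From the Protocol Summary: a study duration of 2 years. From 8.7: reviews at least every 6 months.

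**The plan's own figure.** Section 10.5 gives 22 per group with power 0.822. The Walters approximation is

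power = Φ{ √(2n) × [arcsin√(p1 − 1/(2n)) − arcsin√(p2 + 1/(2n))] − 1.96 }.

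With n = 22, 1/(2n) = 0.0227, so the bracket is arcsin√0.5773 − arcsin√0.1727 = 0.863 − 0.429 = 0.434. Then √44 × 0.434 = 2.88, and Φ(2.88 − 1.96) = 0.822. The figure reproduces.

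**Timing of reviews.** 24 months / 6 = 4, so three reviews fall before the end. With even accrual (assumed, since the protocol gives no schedule), 22 × 1/4, 1/2 and 3/4 gives about 5, 11 and 16 evaluable per arm.

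**How often the letters reveal the arm.** With X ~ Bin(n, p1) on active and Y ~ Bin(n, p2) on placebo,

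P(active ahead) = Σ_i P(X = i) × P(Y < i).

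For n = 5 at 60% vs 15%: 0.0768×0.4437 + 0.2304×0.8352 + 0.3456×0.9734 + 0.2592×0.9978 + 0.0778×0.9999 = 0.899. The tie probability is 0.075 and the wrong arm leads with probability 0.025. The other cells follow the same way.

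| True rates | n per arm | Active ahead | Tie | Active ahead by 2 or more |
|---|---|---|---|---|
| 60% vs 15% (protocol) | 5 | 0.899 | 0.075 | 0.721 |
| 60% vs 15% (protocol) | 11 | 0.984 | 0.012 | 0.953 |
| 35% vs 15% (assumed) | 5 | 0.650 | 0.225 | 0.353 |
| 35% vs 15% (assumed) | 11 | 0.807 | 0.108 | 0.641 |

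At 60% vs 15% and 16 per arm, the active arm is ahead with probability 0.996.

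**Type I error if a review could stop the trial.** The documents state no rule, so I assumed stopping at two-sided Fisher p ≤ 0.05 at 5, 11, 16 or 22 per arm. Exact recursion over the binomial counts gives:

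| Common rate | Single final test | Any of the four looks |
|---|---|---|
| 15% | 0.0222 | 0.0324 |
| 20% | 0.0242 | 0.0407 |
| 30% | 0.0238 | 0.0486 |
| 37.5% | 0.0224 | 0.0523 |
| 50% | 0.0229 | 0.0571 |

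**Exaggeration under the same rule.** At 35% vs 15%, 17.1% of trials would stop early. Their mean observed difference would be 50 points, against a true 35 − 15 = 20.

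**The case against.** Several points on the other side have weight.

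- **Container labels.** Sections 6.1.2 and 6.1.4 describe the containers as unlabeled, while 10.6.1 puts the arm letter on them. The sections should be reconciled. Unlabeled can be read as carrying no product name, and the A/B variable in 10.3 supports the reading used here. Even with no letter on any container, 8.7 would still show investigators efficacy by arm.
- **Coded samples.** Swabs and plates carry only a study code (7.2.3), and growth on a selective plate is fairly objective. Biased culture reading therefore requires linking code to arm. That limit holds for other laboratory staff. It does not protect against the PI and co-investigator, who hold the link file and enter results.
- **Shared roles.** Other team members also recruit, and four people may obtain consent. The PI and co-investigator are not the only route for bias, but they are a main one.
- **Dependence on effect size and accrual.** The inference weakens if the drug does little. At 25% vs 15% and 11 per arm, the active arm leads by two or more only 41% of the time, and 8% of the time the other arm does.
- **Type I error.** At the 15% rate it stays below 5% even with four looks, so this part would not justify a required change on its own.
- **Section 5.8.** It lists circumstances that may warrant stopping and schedules no look. A boundary might appear in the stand-alone SAP announced in 10.1, which was not supplied. That document would not by itself change who attends the 8.7 review.
- **Site-specific outcome.** Section 8.7 names results by body site, which 4.2.3 treats as exploratory. They would still largely reveal the combined endpoint.

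None of this removes the conflict between 8.7 and sections 10.6.1 and 10.4.7.2.

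**Conclusion.** The concern holds and should be fixed before the reviews take place. The contradiction lies in the text and needs no assumption. How likely it is to unmask the trial does rest on assumptions: even accrual over two years, and an effect near the design value. On those, the leading letter is the active one with probability about 0.90 at the first review and 0.98 at the second. At 35% vs 15% this falls to 0.65 and 0.81, so unblinding is a likely inference rather than a certainty. The harm that matters is loss of masking among people who can influence recruitment, follow-up and data entry. The effect on type I error is modest (2.2% to 3.2% at the 15% rate, and at most about 5.7% among the rates checked) and depends on a stopping rule that the documents do not contain.

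**What to change.** - **8.7:** Show the PI and co-investigator pooled data only. Send any by-arm safety listing to the medical monitor alone. Remove by-arm colonization from the semiannual review. State that the monitor's input to the PI and industry partner carries no by-arm figures.
- **5.8:** Delete the efficacy and futility grounds so that the section agrees with 10.4.7. If an efficacy stop is wanted, pre-specify the look and its boundary in 10.4.7, with review by the medical monitor alone.
- **10.6.1:** Have the pharmacy label containers with participant-specific codes instead of one letter per arm, and reconcile this with 6.1.2 and 6.1.4. Breaking the blind for one participant under 10.6.3 then no longer exposes the rest.
- **10.3:** Keep the assigned-group variable out of the investigators' database until lock. The pharmacy then supplies the A/B column to the blinded analyst.

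The cost is protocol wording, a separate closed listing for the monitor and slightly more pharmacy labelling work. The trial gives up an informal early stop for efficacy or futility. Sample size and treatment are unchanged.

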10.1 Statistical and Analytical Plans (SAP)

There will be a formal Statistical and Analytical Plan (SAP). Partial details as outlined in the below sections, with full SAP created by study biostatistician being part of a stand-alone document. Key elements of the analysis plan are described below.

10.2 Statistical Hypotheses

Primary endpoint

The percent change in nasal/rectal colonization of MRSA from baseline to 1 week after completion of decolonization protocol with retapamulin compared to placebo

Null hypothesis: There will be no difference in reduction of nasal/rectal colonization of MRSA from baseline to 1 week after completion of decolonization protocol between retapamulin compared to placebo

Alternative hypothesis: There will be a 45% difference in reduction in nasal/rectal colonization of MRSA from baseline to 1 week after completion of decolonization protocol with retapamulin compared to placebo

Secondary endpoint

The percent change in nasal/rectal colonization of MRSA from baseline to 4 weeks after completion of decolonization protocol with retapamulin compared to placebo

Null hypothesis: There will be no difference in reduction of nasal/rectal colonization of MRSA from baseline to 4 weeks after completion of decolonization protocol between retapamulin compared to placebo

CONFIDENTIAL

This material is the property of the NYU School of Medicine and Langone Medical Center. Do not disclose or use except as authorized in writing by the study sponsor

Alternative hypothesis: There will be a 45% difference in reduction in nasal/rectal colonization of MRSA from baseline to 4 weeks after completion of decolonization protocol with retapamulin compared to placebo

This analysis will be a superiority trial.

10.3 Analysis Datasets

This will be a triple-blinded randomized Intent to Treat (ITT) clinical trial to assess the effectiveness of retapamulin in children colonized with MRSA under the age of 18 from a pre-specified community in Brooklyn. Participants living in the following zip codes will be eligible: 11024, 11205, 11206, 11211, 11213, 11214, 11218, 11219, 11225, 11230, 11249. Neither the treatment team nor the subject will know the treatment assignments. The outcome will be a dichotomous variable (1 = Yes, patient's swab negative for MRSA, 0 = No, Patient's swab positive for MRSA). We will analyze additional co-variables collected on the data collection form such as age, gender, history of MRSA infections, history of chronic medical conditions/chronic skin conditions, etc. (see Data Collection Form in appendix uploaded into study-related documents).

Information from the data collection form will be entered into an Access database designed for this study to provide a readily electronic version dataset to analyze. The following variables will be included: Assigned group (blinded treatment arm, A/B), age, gender, side effects, application day 1 (Y/N), application day 2 (Y/N), application day 3 (Y/N), application day 4 (Y/N), application day 5 (Y/N), environmental clean (Y/N), history of medical conditions or chronic skin conditions, history of MRSA, history of MRSA in family, recent or concomitant antibiotic use, prior retapamulin use etc. Variables related to safety will also be recorded in the database.

In addition to the ITT analysis, we will conduct a per-protocol analysis of those who completed 4 or 5 days of treatment and analyze similar to the ITT analysis.

10.4 Description of Statistical Methods

10.4.1 General Approach

The design of the study is a randomized, double-blind, placebo-controlled clinical trial. Schematic of Study design on page 2 of this document illustrates further.

This will be a double-blinded randomized Intent to Treat (ITT) clinical trial to assess the effectiveness of retapamulin in children colonized with MRSA under the age of 18 from a pre-specified community in Brooklyn. The outcome will be a dichotomous variable (1 = Yes, patient's swab negative for MRSA, 0 = No, Patient's swab positive for MRSA). We will analyze additional co-variables collected on the data collection form such as age, gender, history of MRSA infections, history of chronic medical conditions/chronic skin conditions, etc. (see Data Collection Form in appendix uploaded into study-related documents). These will be presented as descriptive statistics between Retapamulin and Placebo groups and assessed for potential statistical differences between the groups. Chi-square will be used for dichotomous variables and a T-test will be used for continuous variables (if normally distributed otherwise Mann-Whitney).

10.4.2 Analysis of the Primary Efficacy Endpoint(s)

To assess the primary dichotomous endpoint, the change in nasal/rectal colonization of MRSA from baseline to 1 week after completion of decolonization protocol with retapamulin compared to placebo, we will use a fisher exact (non-parametric) to evaluate for significant difference in colonization after 1 week between the two groups. We will provide the difference in decolonization rates with an odd ratio, 95% confidence interval and p-value. Participants will be selected to treatment group at random, therefore baseline characteristics should not significantly differ. However if the two treatment groups have covariates that are significantly different, we will consider a logistic regression to adjust for the difference

CONFIDENTIAL

This material is the property of the NYU School of Medicine and Langone Medical Center. Do not disclose or use except as authorized in writing by the study sponsor
Interventional Template Version: 28 APR 2017

in population. Before we analyze with a logistic regression, we will test for normality to assure that all apriori statistical assumptions are met.

10.4.3 Analysis of the Secondary Endpoint(s)

To assess the secondary dichotomous endpoint, the change in nasal/rectal colonization of MRSA from baseline to 4 week after completion of decolonization protocol with retapamulin compared to placebo, we will use a fisher exact (non-parametric) to evaluate for significant difference in colonization after 4 week between the two groups. We will provide the difference in decolonization rates with an odd ratio, 95% confidence interval and p-value. Participants will be selected to treatment group at random, therefore baseline characteristics should not significantly differ. However if the two treatment groups have covariates that are significantly different, we will consider a logistic regression to adjust for the difference in population. Before we analyze with a logistic regression, we will test for normality to assure that all apriori statistical assumptions are met.

